18.1.2.5 Conversion of time intervals

If a time interval was calculated in minutes, hours or days and needs to be converted into months or years, the following conversion factors will be used:

- 1 month = 30 days
- 1 year = 365.25 days

18.1.2.6 Presentation of units

If applicable, parameters will be displayed together with the used unit of measurement. The unit of measurement is enclosed in square brackets ([]).

18.1.2.7 Presentation of dates

Where applicable (e.g., in listings), dates will be displayed in ISO8601 format (example: 2014-09-29T12:16, see CDISC 2013). In case of incomplete dates, both the original value and the imputed value (if available) is displayed.

18.1.2.8 Handling of missing values

At each time point/visit, all subjects still in the trial are reported. Missing values will be taken into account as missing in the analysis. The number of observed values and the number of missing values must sum up to the number of subjects in the trial at the respective time point/visit.

If missing values are imputed, the result of all imputation strategies and newly derived information must be stored in the ADaM data set. The shifts required for the shift tables should already be included in the ADaM data set.

Imputed values will be listed in the subject data listing and be marked as imputed.

18.1.2.9 Visit time windows

See Section [5.1](#).

18.1.2.10 Trial phases and periods*Treatment Period*

- The Treatment Period start date is the allocation date as documented on the *Allocation to Treatment page* in the eCRF.

- The Treatment Period end date is the date of the End of Treatment Visit as documented in the eCRF.

Tapentadol Period

- The Tapentadol Period start date is the date of the End of Treatment Visit as documented in the eCRF.
- The Tapentadol Period end date is the date assessed on the *End of Period* page of the eCRF at the end of the Tapentadol Period.

Observation Period

- For subjects entering the Observation Period after Part 1, the Observation Period start date is the date of the End of Treatment Visit as documented in the eCRF.
- For subjects who discontinue the Tapentadol Period and enter the Observation Period during Part 2, the Observation Period start date is the date assessed on the *End of Period* page in the eCRF at the end of the Tapentadol Period.
- The Observation Period end date is the date of Visit F12M. If Visit F12M is not performed, the date assessed on the End of Trial page of the eCRF will be used.

18.1.2.11 First and last IMP intake

The first and last IMP intake of the Treatment Period and of the Tapentadol Period will be specified based on the start and end dates provided on the IMP dispense form of the eCRF, supported by the eDiary data.

First IMP intake of the Treatment Period

The first IMP intake of the Treatment Period will be the date and time of the day (morning/evening) of the earliest start entry in the eCRF for the Treatment Period.

The time will be set to the time of the corresponding eDiary entry at that date and time of the day if available; else the time will be missing.

First IMP intake of the Tapentadol Period

The first IMP intake of the Tapentadol Period will be the date and time of the day of the earliest start entry in the eCRF for the Tapentadol Period.

The time will be set to the time of the corresponding eDiary entry at that date and time of the day if available; else the time will be missing.

Last IMP intake of the Treatment Period

The last IMP intake of the Treatment Period will be the date and time of the day of the latest end entry in the eCRF for the Treatment Period.

The time will be set to the time of the corresponding eDiary entry at that date and time of the day if available; else the time will be missing.

Last IMP intake of the Tapentadol Period

The last IMP intake of the Tapentadol Period will be the date and time of the day of the latest end entry in the eCRF for the Tapentadol Period.

The time will be set to the time of the corresponding eDiary entry at that date and time of the day if available; else the time will be missing.

In case the required information from the IMP Dispense form of the eCRF is not available, the first and last IMP intake assigned to the Treatment and Tapentadol Period in the eDiary will be used. In case the switch of the eDiary from the Treatment Period to the Tapentadol Period was missed, the date of Visit VE will be used for the last IMP intake of the Treatment Period and the first IMP intake of the Tapentadol Period, with time of the day and time missing.

18.1.3 Population heterogeneity during Part 2

For Part 2, the different periods, i.e., Tapentadol Period and Observation Period, are not comparable. Subjects in the Tapentadol Period continue to receive tapentadol throughout this period, while patients in the Observational Period do not receive any further IMP. One part of subjects are expected to enter the Observational Period because they are no longer in need of treatment with tapentadol because of an improvement of the underlying pain condition. Other subjects may enter the Observation Period due to worsening of the underlying disease. Subjects may therefore not be sufficiently treated in the Tapentadol Period as they may require higher doses or a different route of administration. Due to the heterogeneity of the subject populations during Part 2 of the trial, no comparisons between the Tapentadol Period and Observation Period will be performed.

18.1.4 Disposition

18.1.4.1 Subject discontinuation

Reasons for subject discontinuation as specified in the End of Trial page or End of Period page of the eCRF.

Completion status

Treatment completer:

- Part 1:
 - If $(End\ of\ Treatment\ Visit\ date - First\ IMP\ intake\ of\ the\ Treatment\ Period\ date) \geq 13$ and either $(Last\ IMP\ intake\ of\ the\ Treatment\ Period\ date - First\ IMP\ intake\ of\ the\ Treatment\ Period) \geq 13$ or $(Last\ IMP\ intake\ of\ the\ Treatment\ Period\ date - First\ IMP\ intake\ of\ the\ Treatment\ Period) = 12$ with last IMP intake of the Treatment Period in the evening.
- Part 2, Tapentadol Period only:
 - If $(F12M\ date - End\ of\ Treatment\ Visit\ date) \geq 351$ with F12M completed as part of Tapentadol Period.

Trial completer:

- Part 1: Treatment completer Part 1 with either
 - Visit F7D performed, if subject entered Observation Period or
 - Subject entered Tapentadol Period
- Part 2: Either

- Treatment completer Part 2 with Visit F7D performed or
- Subjects with F12M of the Observation Period performed with $(F12M \text{ date} - \text{End of Treatment Visit date}) \geq 351$

Time to discontinuation

Time to treatment discontinuation will be calculated in days for Part 1 as:

$$\text{date of Last IMP intake of the Treatment Period} - \text{date of First IMP intake of the Treatment Period} + 1$$

Time to treatment discontinuation will be calculated in weeks for Part 2 as:

$$(\text{date of Last IMP intake of the Tapentadol Period} - \text{date of First IMP intake of the Tapentadol Period} + 1)/7$$

Censoring algorithm

Censoring algorithm is defined as follows:

- Time to IMP discontinuation:
 - Part 1: time will be censored at the date of last IMP intake of the Treatment Period for treatment completers Part 1.
 - Part 2, Tapentadol Period: time will be censored at the date of last IMP intake of the Tapentadol Period for treatment completers Part 2.

18.1.4.2 Protocol deviations

Protocol deviations are based on the analysis data set ADDV. Major protocol deviations are retrieved from the respective SDTM data set (DV.DVCAT). No further protocol deviations are programmed in the analysis data sets for ADDV.

18.1.5 Demographics and other baseline characteristics

18.1.5.1 Subject demographics

Derivation of age

Age as entered directly in the eCRF and available in DM.AGE.

Derivation of BMI:

The BMI is not in the SDTM data set and will be derived from WEIGHT [KG] and HEIGHT[M] of the DM data set. BMI is calculated and rounded to 1 decimal place using the following formula:

$$\text{BMI [KG/M}^2\text{]} = \text{WEIGHT [KG]} / \text{HEIGHT}^2\text{[M]}$$

18.1.5.2 Other baseline characteristics

Derivation of height Z-Scores

The height Z-Scores will be calculated using the WHO Child Growth Standards. The Z-scores can be calculated using the algorithm as implemented in the SAS igrowup package (www.who.int/childgrowth/software/en/) and the required reference files for subjects from 6- <18 years old provided by the WHO (http://www.who.int/growthref/who2007_height_for_age/en/).

As age in months is required for this calculation, it will be derived by multiplying the recorded age in years by 12 and adding 6 months.

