12.2 Collection of subject characteristics data

12.2.1 Demographic data

Demographic data (date of signing the informed consent/assent form, sex, age, and race/ethnicity) will be recorded in the CRF.

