- Analysis of exposure adjusted incidence rates was limited to TEAEs of the Tapentadol Period:
 - Due to the short treatment duration of 14-days only and very low rate of discontinuations during the Treatment Period
 - And as AEs assigned to the Observation Period are not considered treatment-emergent. Furthermore, the presentation of confidence intervals for the difference in incidence rates was discarded due to the reduced sample size and the following limited value of information.
- A summary of the height Z-Scores was added to Part 2. Converting heights to Z-score allows for a comparison of heights across ages and sexes and therefore better evaluation over time.
- Description of the multiple imputation approach was improved to provide clearer programming instructions.

Some further minor adaptations (e.g. adding further details or clarifications to individual analyses, rewordings) and minor editorial changes (e.g., the correction of typing errors or format changes) are not specified here.

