11.1 Subject demographics

Subjects demographics are age [years], body mass index (BMI) [kg/m²], sex, race, ethnicity and age group. Age groups will be 6-<12 years and 12-<18 years.

Weight and height will be collected several times during the trial and will be analyzed separately as safety parameters. The assessments of height and weight at the Enrollment Visit (Visit 1) will be used for the calculation of the BMI. For completeness, baseline values of height and weight are tabulated with subject demographics as well.

Age will be collected at visit V1, V2 and VE.

- Age at Visit V2 will be used for subject demographics of both parts.

Date of signing the informed consent/assent form will be included in the subject data listings only.

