15.2.7 Height

Part 1

Assessments of height and changes from baseline will be summarized descriptively by age subgroups for each visit. In addition to the presentation by treatment arm, descriptive summaries will also be presented overall.

Part 2

Assessments of height and changes from baseline will be summarized descriptively by age subgroups. The patient's height will be transformed into an age and sex adjusted Z-score. The Z-score and change from baseline in Z-score will be summarized by visit, by treatment arm and overall.

Details on the programming aspects regarding the height Z-Score can be found in Section [18.1.5.2](#).

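### As written, the SAP scores every Part 2 height at one fixed age, so the by-visit change in height Z-score is not age-adjusted: no growth shows 0 and normal growth shows a false rise

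*SAP*

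**What the plan says.** SAP 15.2.7 states that in Part 2 the patient's "height will be transformed into an age and sex adjusted Z-score", and then: "The Z-score and change from baseline in Z-score will be summarized by visit, by treatment arm and overall". The rationale for SAP Amendment 01 (SAP 7.2) gives the purpose: "Converting heights to Z-score allows for a comparison of heights across ages and sexes and therefore better evaluation over time".

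The derivation is in SAP 18.1.5.2. It uses the WHO growth algorithm with "the required reference files for subjects from 6- <18 years old". Because that algorithm needs age in months, "it will be derived by multiplying the recorded age in years by 12 and adding 6 months".

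On where age comes from, SAP 11.1 says "Age will be collected at visit V1, V2 and VE". Neither the Tapentadol Period schedule nor the Observation Period schedule has a row for recording age. Protocol 12.2.1 lists the demographic items as "Demographic data (date of signing the informed consent/assent form, sex, age, and race/ethnicity"; date of birth is not among them. SAP 18.1.5.1 points to the age entered in the eCRF.

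Part 2 heights are scheduled at TP3, TP6, TP9, TP12, ET and F12M in the Tapentadol Period, and at OPx and F12M in the Observation Period.

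**The concern.** A height Z-score shows whether a child keeps pace with children of the same age and sex. For a change over time to carry that meaning, the reference must move forward as the child ages. The written rule converts the recorded age and adds a constant 6 months. It does not say which visit's age to use, and nothing advances the age to the date of the height. Every Part 2 height of a subject is then set against the same reference median and SD.

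The output would answer whether the child grew, not whether the child kept up. Zero, which should mean that the child stayed on the same centile, would instead mean no growth at all. Staying on the centile would appear as a gain that increases with follow-up. Describing long-term safety is the only objective of Part 2, and a growth summary that cannot show a child falling behind could be misread as reassuring.

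**Working it through.** The plan gives no numerical result for the Z-score, so there is no figure to reproduce. The check applies the written rule.

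**Inputs from the documents**
- Age in months = 12 × recorded age + 6 (SAP 18.1.5.2).
- Age recorded at V1, V2 and VE only (SAP 11.1).
- Height visits: TP3, TP6, TP9 and TP12 on days 84, 168, 252 and 336; F12M on day 365 (schedule of events).
- Tapentadol Period baseline: last value at or before VE (SAP 8.2.2).

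**Assumptions, not in the documents**
- Reference growth g: 4 to 6 cm/year; 0 to 1 cm/year near adult height.
- Reference SD: 5.5 to 7 cm, held constant over the year.

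**Step 1: the age used.** A recorded age of 6, 9, 12, 15 or 17 gives 78, 114, 150, 186 or 210 months, and the same value at every later visit.

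**Step 2: the change under the written rule.** With Z = (H − M(age))/SD(age) and age fixed at a0, the median cancels:

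change = (H1 − H0)/SD(a0)

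- No growth: H1 = H0, so the change is exactly 0. This needs the same recorded age at baseline and follow-up; a baseline height from V1 with a birthday before VE would be an exception.
- Growth along the reference: the true change is 0, but the rule gives g × (day/365.25)/SD.

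**Step 3: size of the false rise.** The low end is 4 cm/year with SD 7; the high end is 6 cm/year with SD 5.5.

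| Visit | Day | Low | High |
|---|---|---|---|
| TP3 | 84 | 0.13 | 0.25 |
| TP6 | 168 | 0.26 | 0.50 |
| TP9 | 252 | 0.39 | 0.75 |
| TP12 | 336 | 0.53 | 1.00 |
| F12M | 365 | 0.57 | 1.09 |

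Near adult height the upper value at F12M is 1 × (365/365.25)/5.5 = 0.18. Over a wider range (1 to 8 cm/year, SD 8 to 5 cm) the F12M value runs from 0.12 to 1.6.

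**Step 4: the constant 6 months.** It is identical at every visit, so it largely cancels in the change. It is not the fault.

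**Step 5: with age advanced by elapsed time.** A child aged 9 at VE is scored at 114 months at VE and at 114 + 365/30.44 = 126.0 months at F12M. Growth along the reference then gives a change of 0. No growth gives −g × (365/365.25)/SD, that is −0.57 to −1.09 under the Step 3 assumptions.

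**Step 6: whole-year updating would not be enough.** If birthdays are spread evenly, 84/365.25 = 23% of subjects would jump by 12 months by TP3 and the rest would not move.

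**The case against.** The best counter-argument is that the SAP is silent rather than wrong. The formula is a unit conversion and does not forbid adding elapsed time. SAP 15.2.7 asks for an age-adjusted score by visit, so a careful programmer might advance the age unprompted. That is why the point is stated for a literal reading. But SAP 18.1 exists to give technical detail for the SAS code, and nothing in it tells the programmer to do this. The one explicit Part 2 age rule, in SAP 18.1.12 for laboratory, vital-sign and ECG reference ranges, fixes age at VE. Following that precedent would produce this error.

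Second, the output is minor. Height Z-score is not a protocol endpoint, the three-monthly heights were added for calculating glomerular clearance (Protocol Amendment 02 rationale), no safety tests are planned (SAP 15), and raw height and its change by age subgroup are still reported. All of this stands and limits the importance of the point.

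Third, the size rests on assumed growth and SD. The simple formula is exact only for a child at the median or if the SD does not change with age. Subjects who switch to the Observation Period have their baseline at ET, so their interval is shorter. Only 25% of subjects must be under 12, so the cohort average could lie well below the upper figures. This also stands.

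Finally, the wording on the reference files describes the subjects' age range, so an upper limit of the files at 216 months is inferred. The rule proposed for those ages therefore has to allow for files that extend further.

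**Conclusion.** The concern holds. Followed as written, the plan does not deliver the age-adjusted change that SAP 15.2.7 promises. The direction is certain wherever the reference is still rising: each subject's change is shifted upward by the growth expected since baseline, divided by the SD. At F12M that is about +0.57 to +1.09 SD for growing children and 0 to +0.18 SD near adult height, on the assumed growth rates and a constant SD of 5.5 to 7 cm.

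The damage is confined to the within-arm change over time in one descriptive Part 2 safety summary. The primary analysis is untouched. The point should be corrected because it defeats the stated reason for adding the output and is cheap to repair.

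**What to change.** In SAP 18.1.5.2:

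1. Name age at VE as the source, and define age in months at each Part 2 height as 12 × (age at VE) + 6 + (visit date − VE date)/30.44.
2. Note 30.44 (365.25/12, from the SAP's own year length) as an exception to "1 month = 30 days" in SAP 18.1.2.5. The difference is small: 365/30 = 12.17 months against 365/30.44 = 11.99, or 0.18 month, at most about 0.02 SD at 6 cm/year and SD 5.5.
3. State how heights are handled once the derived age reaches 216 months: either use reference values that cover that age, or list those heights without a Z-score. A subject recorded as 17 at VE starts at 210 months, reaches 216 at about day 183 (6 × 30.44), and is at 218.3 at TP9, 221.0 at TP12 and 222.0 at F12M.

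It would help to add that the VE-age rule in SAP 18.1.12 for reference ranges does not apply to the height Z-score.

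The cost is two or three sentences and the matching program change. Visit dates are already collected, so no new data are needed.

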18.1.5.3 Baseline pain intensity of the Treatment Period

According to the protocol, the first dose of IMP should be taken during Visit V2, within 24 hours after randomization. Therefore, the actual day of first IMP intake is not necessarily the same as the day of randomization, but might be the day after the randomization. Based on this, from a programming perspective baseline pain will be derived as follows:

- The pain assessment in the eDiary on the day and at the day time (morning/evening) of the first IMP intake of the Treatment Period will be used as baseline pain.
- In case this eDiary entry is missing, the last available pain assessment before this time point will be used.
- In case this eDiary entry is missing and there is no earlier pain assessment available, baseline pain will be set to missing.

18.1.5.4 Medical history

Not applicable.

18.1.5.5 Prior and concomitant medication or therapy**Assignment of categories “prior” and “concomitant”****Part 1:**

The following rules are used to define the categories “prior” and “concomitant” medication.

Prerequisite is a complete date of first dose of IMP.

Date of medication	Condition	Category
Complete stop date is available	stop date is earlier than date of first dose of IMP	prior
Stop date with missing month	year of stop date is earlier than year of first dose of IMP	prior
Stop date with missing day	month/year of stop date are earlier than month/year of first dose of IMP	prior
Complete start date is available	Start date is later than Visit VE	Not considered for Part 1
start date with missing month	Year of start date is later than year of Visit VE	Not considered for Part 1
start date with missing day	month/year of start date is later than month/year of Visit VE	Not considered for Part 1
Otherwise		concomitant

Part 2:

For all presentations except displaying subjects in the Observation Period that have switched from the Tapentadol Period to the Observation Period, the following rules apply to define the categories “prior” and “concomitant” medication.

Medication ticked as “continued” will be classified as concomitant for the Observation Period and also for the Tapentadol Period if considered (see below).

Date of medication	Condition	Category
Complete stop date is available	Stop date is earlier than or equal to date of Visit VE	prior
Stop date with missing month	Year of stop date is earlier than year of Visit VE	prior
Stop date with missing day	Month/year of stop date are earlier than month/year of Visit VE	prior
Tapentadol Period: Complete start date is available	Only applicable for subjects that discontinue from the Tapentadol Period and switch to the Observation Period: Start date is later than Visit ET	Not considered for Tapentadol period
Tapentadol Period: Start date with missing month	Only applicable for subjects that discontinue from the Tapentadol Period and switch to the Observation Period: Year of start date is later than year of Visit ET	Not considered for Tapentadol period
Tapentadol Period: Start date with missing day	Only applicable for subjects that discontinue from the Tapentadol Period and switch to the Observation Period: month/year of start date is later than month/year of Visit ET	Not considered for Tapentadol period
otherwise		concomitant

For presenting subjects of the Observation Period that have switched from the Tapentadol Period to the Observation Period, the following rules apply to define the categories “prior” and “concomitant” medication.

Medication ticked as “continued” will be classified as concomitant.

Date of medication	Condition	Category
Complete stop date is available	Stop date is earlier than date of Visit ET	prior
Stop date with missing month	Year of stop date is earlier than year of Visit ET	prior
Stop date with missing day	Month/year of stop date are earlier than month/year of Visit ET	prior
otherwise		concomitant

Assignment of flag for medication/therapy taken during IMP administration

Part 1:

The following rules are used to identify medications or therapies which were taken during IMP administration of the Treatment Period of Part 1.

Prerequisite is a complete date of last dose of IMP for the Treatment Period.

Start of medication or therapy date	Condition	Flag for medication during IMP administration
Medication/therapy is not a concomitant medication of Part 1		no
complete date is available	start date is later than date of last dose of IMP, but before Visit VE	no
Otherwise (due to short Treatment Period)		yes

Part 2:

The following rules are used to identify medications or therapies which were taken during IMP administration of the Tapentadol Period of Part 2.

Prerequisite is a complete date of last dose of IMP for the Tapentadol Period.

Start of medication or therapy date	Condition	Flag for medication during IMP administration
Medication/therapy is not a concomitant medication of the Tapentadol Period of Part 2		no
complete date is available	start date is later than date of last dose of IMP	no
missing month	year of start date is later than year of last dose of IMP	no
missing day	month/year of start date are later than month/year of last dose of IMP	no
Otherwise		yes

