10.5.1 Allowed prior and concomitant medications/therapies

Allowed concomitant medications/therapies with timely or dose restrictions are:

On the day of allocation to IMP (Visit V2):

- Weak and strong opioids up to a morphine-equivalent dose of <3.5 mg/kg per day.

During the Treatment Period (from Visit V2 to Visit VE):

- Rescue medication (morphine oral solution) provided by the sponsor.

During the Treatment Period (from Visit V2 to Visit VE) and Tapentadol Period (from Visit VE until Visit ET/Visit F12M):

- Intravenous opioids during surgery.

During the Tapentadol Period (from Visit VE until Visit ET/Visit F12M):

- Immediate release strong opioids for treatment of breakthrough pain and incidental pain.

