11.1.2.3 Visit ET (Early Termination Visit)

Visit ET must be performed within 3 days after last intake of IMP if IMP is stopped before Visit F12M in Part 2. If Visit F12M and Visit ET are performed on the same day, assessments scheduled for both visits will not be repeated at Visit F12M.

The following procedures will be performed:

- Record concomitant medication intake/therapies.
- Perform a physical examination, document that it was performed, and record changes to previous assessment.
- Record height.
- Record body weight.
- Record vital signs (respiratory rate, systolic and diastolic blood pressure, and pulse rate).
- Complete the following questionnaires:
 - Modified CAS questionnaire.
 - Dispense SOWS questionnaire for completion at home if this is the visit of the last intake of IMP. To be completed once daily until the seventh day after the last intake of IMP. To be collected at Visit F7D.
- Record “pain right now” in the CRF (VAS and FPS-R).
- Take blood for central laboratory (hematology, clinical chemistry).
- Collect urine/perform dip stick urinalysis.
- Perform a urine pregnancy test in female subjects who are post-menarchal or older than 12 years at the time of the scheduled visit.
- Check diary compliance.
- Collect the diary.
- Collect returned IMP.
- Perform drug accountability:
 - Confirm and document compliance with IMP intake.
 - Verify discrepancies with subject, or parent(s), legal guardian(s), or caregiver.
- Assess and record adverse events.

Confidential

Protocol KF5503-66
including Amendment 05

Page 66 of 137
DMS version 9.0
27 Jul 2017

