11.4 Prior and concomitant medication or therapy

Therapies will only be displayed in the subject data listings.

Prior and concomitant medication is collected in the eCRF as per enrollment. For the analysis, the following algorithms will be used to define prior and concomitant medication:

Part 1

- Prior is all medication stopped prior to the first dose of IMP, regardless of its start date.
- Concomitant is any medication not stopped before the first dose of IMP, but with start date not after the End of Treatment Visit of the Treatment Period (Visit VE).
- Medication starting after the End of Treatment Visit of the Treatment Period (Visit VE) will not be assigned to Part 1, but Part 2.

Part 2

For all presentations, except displaying prior and concomitant medication for subjects in the Observation Period that have switched from the Tapentadol Period to the Observation Period:

- Prior is all medication stopped prior to or at the End of Treatment Visit of the Treatment Period (Visit VE), regardless of its start date.
- Concomitant is any medication not stopped before or at the End of Treatment Visit of the Treatment Period (Visit VE) and, for subjects discontinuing treatment early in the Tapentadol Period, with start date not after Visit ET.

For presenting prior and concomitant medication for subjects in the Observation Period that have switched from the Tapentadol Period to the Observation Period:

- Prior is all medication stopped prior to or at the Early Termination Visit (Visit ET) regardless of its start date.
- Concomitant is any medication not stopped before or at Visit ET, regardless of its start date.

Medication will be summarized and sorted alphabetically separately for prior and concomitant medication by Anatomical Therapeutic Chemical categories (Level 2: pharmacological or therapeutic subgroup and Level 3: chemical or therapeutic or pharmacological subgroup). For each medication the number of subjects will be displayed. In addition the number of subjects with medication taken during IMP administration for the Treatment and Tapentadol Period (flag definition see Section 18.1.5.5) will be displayed.

Medication or therapy taken during IMP administration for the Treatment Period of Part 1 as well as medication or therapy taken during IMP administration for the Tapentadol Period of Part 2 will be flagged in the subject data listing.

Handling incomplete dates is described in Section 18.1.5.5.

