18 APPENDIX

18.1 Programming specifications

18.1.1 Introduction

The purpose of this section is to give technical details for SAP text implemented as Statistical Analysis System (SAS) code.

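### For switchers to the Observation Period, SAP 18.1.5.5 codes a drug stopped on the date of Visit ET as concomitant, while SAP 11.4 defines it as prior

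*SAP*

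**What the plan says.** SAP 11.4 gives a separate definition for subjects in the Observation Period who came from the Tapentadol Period: "Prior is all medication stopped prior to or at the Early Termination Visit (Visit ET) regardless of its start date". Its complement is "Concomitant is any medication not stopped before or at Visit ET, regardless of its start date".

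SAP 18.1.5.5 turns this into a date rule. It opens with "For presenting subjects of the Observation Period that have switched from the Tapentadol Period to the Observation Period, the following rules apply". For a complete stop date, the condition for prior is "Stop date is earlier than date of Visit ET". Further rows handle partial dates, drugs ticked as continuing are concomitant, and whatever is left over is concomitant.

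For all other Part 2 presentations the reference visit is VE, and the corresponding row in 18.1.5.5 reads "Stop date is earlier than or equal to date of Visit VE".

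SAP 18.1.1 describes the role of the appendix: "The purpose of this section is to give technical details for SAP text implemented as Statistical Analysis System (SAS) code". On the timing of the visit, Protocol 11.1.2.3 says "Visit ET must be performed within 3 days after last intake of IMP if IMP is stopped before Visit F12M in Part 2".

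**The concern.** The definition includes the day of Visit ET and the coding rule excludes it, so the same record falls into opposite categories depending on which section is followed. Because the appendix is what gets programmed, the rule that departs from the definition is the one likely to reach the output.

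Switchers are a separately presented Observation Period arm (SAP 8.1), and 11.4 calls for counts of subjects by drug category, split into prior and concomitant. A drug taken past Visit VE, started by ET and stopped on the ET date is concomitant for the Tapentadol Period. Under 18.1.5.5 it would also be counted as concomitant for the Observation Period, where 11.4 calls it prior. The subjects who entered the Observation Period directly are classified with the inclusive VE rule, so the arms of that period would treat the boundary day differently.

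**Working it through.** The plan gives no figure to reproduce. The check applies both rules to the same stop dates.

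**Rules for a complete stop date**

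- SAP 11.4: prior if stop date ≤ date of ET, otherwise concomitant.
- SAP 18.1.5.5, switcher table: prior if stop date < date of ET, otherwise concomitant.

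**Step 1. Stop date relative to ET**

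| Stop date minus ET date (days) | SAP 11.4 | SAP 18.1.5.5 | Agree? |
|---|---|---|---|
| -3 | prior | prior | yes |
| -2 | prior | prior | yes |
| -1 | prior | prior | yes |
| 0 | prior | concomitant | **no** |
| +1 | concomitant | concomitant | yes |
| +2 | concomitant | concomitant | yes |

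The rules differ on one day only, the day of ET itself.

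**Step 2. A drug stopped on the day of the last IMP intake.** Protocol 11.1.2.3 lets ET fall 0 to 3 days after that intake, so the stop date minus the ET date is 0, -1, -2 or -3.

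| ET, days after last IMP intake | SAP 11.4 | SAP 18.1.5.5 |
|---|---|---|
| 0 | prior | concomitant |
| 1 | prior | prior |
| 2 | prior | prior |
| 3 | prior | prior |

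Such a drug is affected only if ET is held on the day of the last intake.

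**Step 3. Which passage is out of line?** Each coding row can be set against its own definition in 11.4.

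| Presentation | Definition in 11.4 | Coding in 18.1.5.5 | Match? |
|---|---|---|---|
| Part 1, first IMP dose | strictly before | strictly before | yes |
| Part 2, Visit VE | before or on | before or on | yes |
| Part 2 switchers, Visit ET | before or on | strictly before | **no** |

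Only the ET row departs from its definition. SAP 8.2.2 also places ET on the earlier side of the boundary: the Observation Period baseline for switchers is the last evaluation up to and including Visit ET.

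**Step 4. After the change.** With an inclusive comparison in the ET row, the line for 0 in Step 1 becomes prior under both rules, and the two sections agree for every complete stop date.

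**The case against.** The strongest reply is that very little turns on this. It concerns one calendar day, complete dates only, one arm, and descriptive tables. SAP 18.1.3 rules out comparisons between the Tapentadol and Observation Periods. The flag in 11.4 and 18.1.5.5 for medication taken during IMP administration would also mark, in the listing, a drug begun on tapentadol and stopped at ET. All of this stands and keeps the point minor. It does not remove the contradiction: the flag shows overlap with IMP, but the prior or concomitant category in the table would still differ from the definition.

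It could also be argued that the strict rule is deliberate, because the ET date may be both the last day of one period and the first of the next. The same is true of Visit VE for direct entrants, since SAP 18.1.2.10 starts their Observation Period on the VE date. There the SAP treats a drug stopped on the shared day as prior.

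A reader might go further and infer three things that the documents do not support:

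- **That drugs which ended with tapentadol will appear as use after it, use that never took place.** This holds only when ET falls on the day of the last intake. If ET is 1 to 3 days later, a drug stopped with the last tapentadol dose is prior under both rules, and a drug stopped on the ET date really did run past the last dose.
- **That breakthrough opioids must end at ET, so stop dates will cluster there.** Protocol 10.5.1 lists "Immediate release strong opioids for treatment of breakthrough pain and incidental pain" as allowed in the Tapentadol Period because 10.5.2 otherwise forbids non-trial opioids while IMP is taken. Protocol 10.5 limits these restrictions, where appropriate, to subjects taking IMP, and 11.5 leaves later care to local standard treatment. Nothing requires an opioid to stop at ET.
- **That a sizeable share of switchers is affected.** The documents give no basis for any percentage. A subject also adds to the count for a drug category only if no other drug in that category continues after ET.

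**Conclusion.** The inconsistency is in the current SAP text and is certain: 11.4 and 18.1.5.5 give opposite categories to every drug in the switcher arm with a complete stop date equal to the ET date, and agree on every other complete stop date. That the ET row is a slip is an inference, but a firm one, since the other two coding rows match their definitions.

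The reach is the category assignment and the descriptive medication tables for switchers. The number of records depends on how many stop dates fall on the ET date, which the documents do not say. The primary endpoint does not use this category. This is a minor correction, worth making because the coded rule would otherwise put those records in the wrong category in a planned table.

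**What to change.** In the switcher table of SAP 18.1.5.5, change the condition for a complete stop date so that it includes the day of Visit ET. It would then have the same form as the VE row ("Stop date is earlier than or equal to date of Visit VE"), with ET in place of VE. No change to 11.4 is needed, and the partial-date rows can stay as they are.

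The cost is one comparison operator in the SAP and the corresponding program. No additional data are required.
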